### 2.1 Trial Design

The study will incorporate Simon's optimal 2-stage design with sample size fixed at 12 subjects each in Stage 1 for advanced melanoma and for Triple Negative Breast Cancer (TNBC) subjects. The safety criterion of  $\leq 4$  (or  $\leq 33\%$ ) subjects with Grade 3/4 adverse events in Cycle 1 within either tumor type must be met in order to proceed to Stage 2. The starting dose is 4 mg/kg for Imprime PGG. In the event there are a total of  $> 4$  (or  $> 33\%$ ) of subjects with Grade 3/4 adverse events in Cycle 1, the dose of Imprime PGG will be reduced to 2 mg/kg, and Stage 1 will be repeated at a dose of 2 mg/kg with an additional cohort of n=12 subjects. For the dose that meets the safety criterion in Stage 1, at least 1 response in melanoma subjects and 1 response in TNBC subjects amongst the 12 subjects within each tumor type must be observed in order to proceed to Stage 2.

Stage 2 will enroll an additional 17 subjects with melanoma, and 29 subjects with TNBC. For the dose that meets the Stage 1 safety criterion, success will be declared if at least 4 amongst the total of up to 29 subjects with melanoma, and 5 amongst the total of up to 41 subjects with TNBC achieve an objective response.

The study population will be those having failed front-line therapy, defined as any treatment regimen or regimens used specifically in the treatment of metastatic disease. Refer to [Section 5.1 on Entry Criteria](#) for the study-specific requirements.

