## 2.2 Trial Diagram

\* ≤ 4 subjects or 33% of Stage 1 subjects does not include infusion reactions (from either study drug) which were subsequently controlled and reduced in Cycle 1 via ameliorating actions, and which did not recur in Cycle 2

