## **3. Dose Reduction**

If a subject experiences an infusion reaction despite having been administered premedication and despite the infusion time being lengthened, the PI may re-challenge the subject at the next visit by dose reducing the Imprime PGG to 2 mg/kg.

All attempts should be made to ameliorate Grade 3/4 infusion reactions by the Investigator following the 3 recommendations provided above sequentially.

In Stage 1, any Grade 3/4 infusion reactions mitigated by these actions and either resolving or decreasing to Grade 1/2, if this mitigation occurs within Cycle 1 and the Grade 3/4 infusion reaction does not recur in Cycle 2, will not be counted towards the total of > 4 or 33% of Grade 3/4 adverse events which require halting the study in Stage 1 for each individual indication. Only Cycle 1 Grade 3/4 infusion reactions (or those which recur in Cycle 2) will be counted towards the total which would halt advancement to Stage 2.

- In the event there are a total of > 4 or 33% of Grade 3/4 adverse events in Stage 1 which were unable to be ameliorated by the sequential recommendations above, the dose of Imprime PGG will be reduced to 2 mg/kg.
- Stage 1 will be repeated with an additional cohort of n=12 subjects at the reduced dose of 2 mg/kg. Toxicity at the dose of 2 mg/kg will be assessed in this additional Stage 1 cohort in the same manner as was done for the initial dose of 4 mg/kg, with the identical sequential recommendations for any observed infusion reactions.
- Advancement to Stage 2 will be halted if there are > 4 or 33% of Grade 3/4 adverse reactions. Otherwise, subjects will proceed to Stage 2 with all subjects at the new, reduced dose of 2 mg/kg.

Note that continuation onto Stage 2 requires a demonstration of at least 1 or 2 objective responses in subjects with melanoma or TNBC, respectively, in addition to meeting the adverse event requirements detailed above, at either Imprime PGG dose of 4 mg/kg or 2 mg/kg. Please refer to the [Trial Diagram](#) in [Section 2.2](#) for a schema of the study flow from start to end.

In general, any Grade 4 non-infusion or non-hematological AE will lead to the withdrawal of the subject from treatment. A dosing delay of up to 3 weeks is allowed in case of Grade 3 non-hematological AEs to reduce toxicity to baseline or Grade 0-1. Dose levels will be adjusted individually for each study drug.

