Grades 3 or 4  Grade 3: Prolonged (ie, not rapidly responsive to symptomatic medication and/or brief interruption of infusion); recurrence of symptoms following initial improvement; hospitalization indicated for other clinical sequelae (eg, renal impairment, pulmonary infiltrates)  Grade 4: Life-threatening; pressor or ventilatory support indicated	
Stop Infusion.            Additional appropriate medical therapy may include but is not limited to:
 
 
Epinephrines**
 
IV fluids
 
Antihistamines
 
NSAIDS
 
Acetaminophen
 
Narcotics
 
Oxygen
 
Pressors
 
Corticosteroids
 
 
Increase monitoring of vital signs as medically indicated until the subject is deemed medically stable in the opinion of the Investigator.            Hospitalization may be indicated.            **In cases of anaphylaxis, epinephrine should be used immediately.  Subject is permanently discontinued from further study drug treatment.
	No subsequent dosing

Appropriate resuscitation equipment should be available at the bedside and a physician readily available during the period of drug administration.

For further information, refer to the Common Terminology Criteria for Adverse Events v4.03 (CTCAE) at <http://ctep.cancer.gov>

In Stage 1, any Grade 3/4 infusion reactions mitigated by these actions and either resolving or decreasing to Grade 1/2, if this mitigation occurs within Cycle 1 and the Grade 3/4 infusion reaction does not recur in Cycle 2, will not be counted towards the total of > 4 or 33% of Grade 3/4 adverse events which require halting the study in Stage 1 for each individual indication. Only Cycle 1 Grade 3/4 infusion reactions not controlled by the above measures (or those which recur in Cycle 2) will be counted towards the total which would halt advancement to Stage 2.

Dose will be managed individually for each study drug.

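### The Stage 1 safety rule is misstated in two places: SAP Section 4 reverses the infusion-reaction exclusion, and Protocol 5.2.1.2.1 and 5.2.1.2.2 total events where the rule counts subjects

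*Protocol*

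**What the plan says.** **Subjects, Cycle 1.** Protocol 2.1 sets a limit of at most 4 (33%) "subjects with Grade 3/4 adverse events in Cycle 1 within either tumor type must be met in order to proceed to Stage 2". Protocol 9.1.1 and the main sentences of SAP Section 4 say the same. Above 4, Imprime PGG drops to 2 mg/kg and Stage 1 is repeated in 12 more subjects.

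**The exclusion in the Protocol.** The footnote to the Section 2.2 diagram says that the limit of 4 "subjects or 33% of Stage 1 subjects does not include infusion reactions (from either study drug"). The reactions left out are those "controlled and reduced in Cycle 1 via ameliorating actions, and which did not recur in Cycle 2". Section 5.2.1.2.1 agrees: a mitigated Grade 3/4 infusion reaction, "if this mitigation occurs within Cycle 1 and the Grade 3/4 infusion reaction does not recur in Cycle 2, will not be counted". Section 5.2.1.2.2, after Table 2, sets the same condition, and both sections add that reactions recurring in Cycle 2 do count.

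**The exclusion in the SAP.** The parenthesis in Section 4 takes Cycle 1 Grade 3/4 infusion reactions that resolve or fall to Grade 1/2 and then recur in Cycle 2. It says that these do not count, and gives the total as 4 or more.

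**Events.** The dose-cut bullet in Protocol 5.2.1.2.1 refers to "a total of > 4 or 33% of Grade 3/4 adverse events in Stage 1 which were unable to be ameliorated". For the 2 mg/kg cohort it reads: "Advancement to Stage 2 will be halted if there are > 4 or 33% of Grade 3/4 adverse reactions". Section 5.2.1.2.2 says that controlled reactions "will not be counted towards the total of > 4 or 33% of Grade 3/4 adverse events which require halting the study".

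**Status.** SAP 5.1 reports in the past tense that the Stage 1 assessment of the safety criterion was done.

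**The concern.** This rule fixes the dose. It decides whether 4 mg/kg goes forward, whether 12 more subjects are treated at 2 mg/kg, and, through Protocol 9.1.3, which dose cohort is tested for response rate. A severe reaction that returns despite mitigation is the kind the rule is meant to catch, and the SAP taken literally discards it. It also gives no relief for a reaction that was successfully controlled, which is what the Protocol's exclusion is for.

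The SAP is the document from which the report will be written. If the report repeats Section 4, it will describe the exclusion backwards. If the team applied the Protocol rule, a reader could take that for a departure from the SAP, since SAP Section 8 requires deviations from planned analyses to be identified.

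**Working it through.** **1. The plan's own threshold.** With 12 Stage 1 subjects (Protocol 2.1, 9.1.1), 4/12 = 33.3% and 5/12 = 41.7%. So the rule passes at 4 and fails at 5. The count of 4 and the 33% agree only when the denominator is 12 subjects. A percentage of adverse events has no stated denominator. This is why the subject count must be the intended rule.

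**2. SAP parenthesis against the Protocol.** Take three groups of different subjects:
- a = subjects with a non-infusion Grade 3/4 event in Cycle 1
- r = subjects with a mitigated Cycle 1 Grade 3/4 infusion reaction that recurs in Cycle 2
- q = subjects with a mitigated reaction that does not recur

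The Protocol counts a + r. The SAP, read literally, counts a + q, because its main sentence counts every affected subject and the parenthesis removes only r. Using more than 4 as the failure threshold for both:

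| a | r | q | Protocol a + r | SAP a + q |
|---|---|---|---|---|
| 3 | 2 | 0 | 5, fails | 3, passes |
| 3 | 0 | 2 | 3, passes | 5, fails |
| 4 | 1 | 0 | 5, fails | 4, passes |
| 4 | 0 | 1 | 4, passes | 5, fails |

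The error can therefore run in either direction, and with 4 non-infusion subjects a single mitigated reaction is enough. The parenthesis's total of 4 or more differs from the rule's more than 4 only when exactly 4 subjects are counted. The first two rows do not depend on which of the two is used.

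**3. Events against subjects, same window and same exclusions.** Let k subjects have e countable events. The readings disagree only when k ≤ 4 and e ≥ 5, so the extra events needed are 5 − k: 1 with k = 4, 2 with k = 3, 3 with k = 2, and 4 with k = 1.
- Four subjects with 2 + 1 + 1 + 1 = 5 events pass by subjects and fail by events.
- Two subjects with 2 events each give e = 4 and pass both ways, so a repeat event in one subject is not enough by itself.

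**4. Stage 1 against Cycle 1.** The dose-cut bullet names Stage 1 and no cycle. Suppose 3 subjects have one Cycle 1 event each and 2 others have one later event each. The Cycle 1 subject rule counts 3 and passes. The literal bullet counts 3 + 2 = 5 and fails, although no subject has two events.

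**5. Efficacy design.** The response-rate design figures are computed without the safety rule. The chance of stopping for no response in 12 at a 5% rate is 0.95^12 = 0.540 (stated as 0.54). Summing the exact binomial over Stage 1 outcomes, with at least 1 response needed to continue, gives:
- melanoma (at least 4 of 29): alpha 0.0500, power 0.902 at 23%
- TNBC (at least 5 of 41): alpha 0.0452, power 0.906 at 21%

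None of these depends on how adverse events are counted.

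**The case against.** The strongest reply is that nobody would have applied the faulty wording. SAP 5.1 says the safety criterion was assessed, and SAP 4, Protocol 2.1 and Protocol 9.1.1 all define that criterion in subjects. A limit of 33% of adverse events cannot be applied as written, and 5.2.1.2.1 itself points to the Section 2.2 diagram, whose footnote counts subjects. The SAP parenthesis looks like a dropped negative. No analysis specified in the SAP uses the exclusion, and the dosing, Grade III/IV and infusion-reaction listings (SAP 12.1, 12.2) allow a recount. The Stage 1 decision is past.

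Much of this stands. The unit applied is not seriously in doubt, so the event wording is loose drafting and not a rival rule. Two neighbouring points also fall away. In 5.2.1.2.1 the sentence "Only Cycle 1 Grade 3/4 infusion reactions (or those which recur in Cycle 2) will be counted towards the total" lacks the qualifier about uncontrolled reactions found in 5.2.1.2.2, but the sentence before it supplies the meaning. Protocol 9.1.1 is silent on the exclusion, but Section 9.1 is a summary.

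The SAP reversal does not fall away. No reading reconciles it with the three Protocol sections, and SAP 5.1 does not say which exclusion was used. Only the footnote of the Section 2.2 diagram was available for this review, but that footnote states the condition plainly.

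A reader might go further and infer that the wrong dose was carried forward, or that the response-rate test is compromised. The documents support neither: they give no Stage 1 counts, and the efficacy boundaries do not involve the safety rule.

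**Conclusion.** The point holds as an internal inconsistency of minor severity. The SAP Section 4 parenthesis is wrong as written, in both its recurrence condition and its threshold. The event and Stage 1 wording in Protocol 5.2.1.2.1, and the event wording in 5.2.1.2.2, do not match the subject rule stated elsewhere.

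The size is given as counts that would flip a decision: one or two subjects with mitigated reactions for the SAP error, and 5 − k extra events among k affected subjects for the unit. These are hypothetical configurations under literal readings. No probability is attached, because the documents give neither a Grade 3/4 rate nor a number of events per subject. What remains uncertain is which infusion-reaction exclusion was used at the Stage 1 assessment.

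**What to change.** 1. In the SAP Section 4 parenthesis, exclude mitigated reactions that do not recur in Cycle 2, and give the total as more than 4.
2. In Protocol 5.2.1.2.1 (including the 2 mg/kg bullet) and 5.2.1.2.2, count subjects with at least one countable Grade 3/4 adverse event in Cycle 1, each subject once. Infusion reactions that recur in Cycle 2 count.
3. Because Stage 1 has been assessed, state in the report for each tumor type which infusion-reaction exclusion was applied, how many subjects were counted, and whether the SAP wording would have changed the decision.

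The cost is one SAP parenthesis, a few words in two Protocol sections, and a short statement drawn from listings already planned. It needs no new data or subjects and changes no efficacy boundary. If a Protocol amendment is no longer worthwhile, items 1 and 3 are still worth making.

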#### 9.1.1 Hypothesis and Study Design

The study design is based on hypothesis testing of the ORR for pembrolizumab + Imprime PGG. For melanoma subjects, the null hypothesis is ORR  $\leq 5\%$ , versus the alternative hypothesis of ORR  $\geq 23\%$ ; for the TNBC subjects, the null hypothesis is ORR  $\leq 5\%$  (ORR=5% in KEYNOTE-086), and the alternative hypothesis is ORR  $\geq 21\%$ . Hypotheses testing will be conducted using a one-sided type I error of 0.05.

The study will incorporate Simon's optimal 2-stage design with sample size fixed at 12 subjects in Stage 1 (for melanoma, Simon's optimal 2-stage design has 12 subjects at Stage 1; for TNBC, a modified Simon's 2-stage design with the sample size fixed at 12 at Stage 1 is used). The safety criterion of  $\leq 4$  (or  $\leq 33\%$ ) subjects with Grade 3/4 adverse events in Cycle 1 within either tumor type must be met in order to proceed to Stage 2. The starting dose is 4 mg/kg for Imprime PGG. In the event there are a total of  $> 4$  (or  $> 33\%$ ) of subjects with Grade 3/4 adverse events in Cycle 1, the dose of Imprime PGG will be reduced to 2 mg/kg, and Stage 1 will be repeated at a dose of 2 mg/kg with an additional cohort of n=12 subjects. For the dose that meets the safety criterion in Stage 1, at least 1 response in

melanoma subjects and 1 response in TNBC subjects amongst the 12 subjects within each tumor type must be observed in order to proceed to Stage 2. The probabilities of early termination at Stage 1 for not achieving such responses are 0.54 and 0.54 if the null hypothesis is observed for melanoma and TNBC subjects, respectively. Stage 2 will enroll an additional 17 subjects with melanoma and 29 subjects with TNBC.

For the dose that meets the safety criterion in Stage 1, rejection of the null hypothesis will require documenting at least 4 objective responses among the total of up to 29 subjects with melanoma and 5 objective responses among the total of up to 41 subjects with TNBC.

The above designs correspond to a type I error 0.05 and power of 90% for both melanoma and TNBC. The PASS 14 Power Analysis and Sample Size System statistical software was used for the study design calculation.

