### **9.1.3 Efficacy Analyses**

Efficacy analysis will be conducted separately for each tumor type. The primary efficacy endpoint is ORR, and the secondary efficacy endpoints include PFS, TTR, CRR, DoR and OS. The primary efficacy population will include all evaluable subjects who receive at least one dose of study treatment, have measurable disease at baseline per RECIST v1.1, and have at least one post-baseline scan or discontinue study treatment as a result of progressive disease, death, or a treatment-related adverse event before the first post-baseline scan.

Hypotheses testing of ORR will be conducted among evaluable subjects at the dose which meets the safety criterion in Stage 1. Among the 12 evaluable subjects in Stage 1, at least 1 objective response in melanoma subjects would be needed to proceed to Stage 2 for melanoma; and at least 1 objective response in TNBC subjects would be needed to proceed to Stage 2 for TNBC. If there are at least 4 objective responses among the total of 29 evaluable subjects with melanoma and/or at least 5 objective responses among the total of 41 evaluable subjects with TNBC, the null hypothesis will be rejected for melanoma and/or TNBC and the study will be declared a success.

The point estimate along with the exact 95% confidence interval will be computed for ORR and CRR. PFS and OS will be summarized descriptively and graphically using the Kaplan-Meier method. The Kaplan-Meier estimate for the median, first, and third quartiles will be determined along with 95% confidence intervals (CIs). The Brookmeyer-Crowley method will be used for the CI calculations. For the subset of subjects who have a CR or PR, TTR and DoR will be summarized similarly using the Kaplan-Meier method. The Kaplan-Meier

estimate of PFS rate at the landmark times of 6 months and 1 year, and the OS rates at the landmark time of 1 year will be calculated.

Exploratory analyses may be conducted using iRECIST.

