#### **9.1.6 Interim Analyses**

One interim analysis will be conducted at the end of Stage 1 for each tumor type. For the dose which meets the safety criterion in Stage 1, if at least 1 objective response among 12 evaluable melanoma subjects is not observed, the melanoma cohort will be terminated; if at least 1 objective response among 12 TNBC evaluable subjects are not observed, the TNBC cohort will be terminated. Early stopping at the interim analysis will only occur for futility, not efficacy. Adverse events including  $\geq$  Grade 3 events will be summarized at the time of the interim analysis.

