4 STUDY DESIGN

This is a Phase 2 study of Imprime PGG and pembrolizumab in subjects with advanced melanoma failing front-line treatment with checkpoint inhibitors or TNBC failing front-line chemotherapy for metastatic disease.

The study design is based on hypothesis testing of the ORR for pembrolizumab + Imprime PGG. For melanoma subjects, the null hypothesis is $ORR \leq 5\%$, versus the alternative hypothesis of $ORR \geq 23\%$; for the TNBC subjects, the null hypothesis is $ORR \leq 5\%$ ($ORR=5\%$ in KEYNOTE-086), and the alternative hypothesis is $ORR \geq 21\%$. Hypotheses testing will be conducted using a one-sided type I error of 0.05.

The study will incorporate Simon's optimal 2-stage design with sample size fixed at 12 subjects each in Stage 1 for advanced melanoma and for TNBC subjects. The safety criterion of ≤ 4 (or $\leq 33\%$) subjects with Grade 3/4 adverse events in Cycle 1 within either tumor type must be met in order to proceed to Stage 2 (Grade 3/4 infusion reactions which occur during Cycle 1 that either resolve or decrease to Grade 1/2 and recur in Cycle 2, will not be counted towards the total of ≥ 4). The starting dose is 4 mg/kg for Imprime PGG. In the event there are a total of > 4 (or $> 33\%$) of subjects with Grade 3/4 adverse events in Cycle 1, the dose of Imprime PGG will be reduced to 2 mg/kg, and Stage 1 will be repeated at a dose of 2 mg/kg with an additional cohort of $n=12$ subjects. For the dose that meets the safety criterion in Stage 1, at least 1 response in melanoma subjects and 1 response in TNBC subjects amongst the 12 subjects within each tumor type must be observed in order to proceed to Stage 2. Stage 2 will enroll an additional 17 subjects with melanoma, and 29 subjects with TNBC. For the dose that meets the Stage 1 safety criterion, success will be declared if at least 4 amongst the total of up to 29 subjects with melanoma, and 5 amongst the total of up to 41 subjects with TNBC achieve an objective response. The above design corresponds to a type I error 0.05 and power of 90% for both melanoma and TNBC.

The dosing schedule and the study assessments are presented in the schedule of assessment in the protocol.

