5 PLANNED ANALYSES

5.1 Interim Analyses

An informal interim analysis was conducted at the end of Stage 1 to assess the safety criterion for each tumor type and confirm the dose of Imprime PGG before continuing enrollment in Stage 2. Overall response rate based on RECIST 1.1 and adverse events including Grade 3/4 adverse events were considered for decision-making. Safety data will be summarized periodically throughout the study as part of ongoing safety review.

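### Protocol Section 5.2.1.2.1 requires 2 TNBC responses to open Stage 2, every other section requires 1, and the stated 90% power holds only with 1

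*Protocol*

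**What the plan says.** The note that closes the Imprime PGG dose-modification text (Protocol Section 5.2.1.2.1, under Dose Reduction) says that "continuation onto Stage 2 requires a demonstration of at least 1 or 2 objective responses in subjects with melanoma or TNBC, respectively". It applies at either Imprime PGG dose and refers the reader to the Trial Diagram in Section 2.2.

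The other statements of the TNBC gate differ from it and agree with each other:

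- Protocol Section 2.1: "at least 1 response in melanoma subjects and 1 response in TNBC subjects amongst the 12 subjects within each tumor type must be observed". Section 9.1.1 repeats the same requirement.
- Protocol Section 9.1.3: "at least 1 objective response in TNBC subjects would be needed to proceed to Stage 2 for TNBC".
- Protocol Section 9.1.6: "if at least 1 objective response among 12 TNBC evaluable subjects are not observed, the TNBC cohort will be terminated".
- SAP Section 4: "at least 1 response in melanoma subjects and 1 response in TNBC subjects amongst the 12 subjects within each tumor type".

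Section 9.1.1 also gives the operating characteristics: "The probabilities of early termination at Stage 1 for not achieving such responses are 0.54 and 0.54 if the null hypothesis is observed", and "The above designs correspond to a type I error 0.05 and power of 90% for both melanoma and TNBC".

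SAP Section 5.1 is in the past tense: "An informal interim analysis was conducted at the end of Stage 1". It says that response rate and adverse events entered the decision, but gives neither a response threshold nor a TNBC response count.

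**The concern.** This is the go/no-go rule for the whole TNBC cohort. The word linking the two numbers to the two tumor types in the Section 5.2.1.2.1 note leaves only one reading: 1 for melanoma, 2 for TNBC. With 0 responses, or with 2 or more, all the texts lead to the same decision. With exactly 1 of 12 they lead to opposite decisions.

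A stricter futility gate cannot raise the type I error, so a false claim of activity is not the risk. What is at stake is power, the probability of early termination, and the chance of abandoning a regimen that works as well as the design hopes. Since the Stage 1 decision has already been taken, the documents should also show that the rule behind the published power was the rule applied.

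**Working it through.** **Inputs** (Protocol Sections 3.1, 9.1.1 and 9.1.3). TNBC: 12 subjects in Stage 1, 29 more in Stage 2, total 41; success at 5 or more responses; null ORR 5%, alternative 21%; one-sided alpha 0.05. The gate k is 1 (Sections 2.1, 9.1.1, 9.1.3, 9.1.6 and SAP Section 4) or 2 (Section 5.2.1.2.1).

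**Formulas.** With X1 ~ Bin(12, p) and X2 ~ Bin(29, p):

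- P(success) = sum over x from k to 12 of P(X1 = x) × P(X2 ≥ 5 − x)
- P(stop at Stage 1) = P(X1 < k)

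**Terms of the sum**, each P(X1 = x) × P(X2 ≥ 5 − x):

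| x | p = 0.05 | p = 0.21 |
|---|---|---|
| 1 | 0.3413 × 0.0548 = 0.0187 | 0.1885 × 0.8861 = 0.1670 |
| 2 | 0.0988 × 0.1751 = 0.0173 | 0.2756 × 0.9598 = 0.2645 |
| 3 | 0.0173 × 0.4292 = 0.0074 | 0.2442 × 0.9906 = 0.2419 |
| 4 | 0.0021 × 0.7741 = 0.0016 | 0.1460 × 0.9989 = 0.1459 |
| ≥5 | 0.0002 | 0.0866 |

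**Gate of 1: the plan's own figures.**

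- Early termination under the null: 0.95^12 = 0.540 (stated 0.54).
- Type I error: 0.0187 + 0.0173 + 0.0074 + 0.0016 + 0.0002 = 0.0452 (stated 0.05).
- Power: 0.1670 + 0.2645 + 0.2419 + 0.1459 + 0.0866 = 0.9059 (stated 90%).

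All three reproduce. So does melanoma (at least 1 of 12, then at least 4 of 29, alternative 23%): early termination 0.540, type I error 0.0500, power 0.902.

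**Gate of 2.** The x = 1 row drops out.

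- Early termination under the null: 0.5404 + 0.3413 = 0.882 (rounded).
- Type I error: 0.0452 − 0.0187 = 0.0265.
- Power: 0.9059 − 0.1670 = 0.7389.

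| | Stated | At least 1 of 12 | At least 2 of 12 |
|---|---|---|---|
| Type I error | 0.05 | 0.0452 | 0.0265 |
| Power at 21% | 90% | 0.906 | 0.739 |
| Early termination at 5% | 0.54 | 0.540 | 0.882 |
| Early termination at 21% | not stated | 0.059 | 0.248 |
| Expected N at 5% | not stated | 25.3 | 15.4 |

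Expected N is 12 + 29 × (1 − early termination probability at 5%).

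**Could another final cutoff or sample size rescue a gate of 2?** No. Power cannot exceed P(X1 ≥ 2) at 21%, which is 1 − 0.248 = 0.752, whatever the Stage 2 size or final cutoff. The stated 90% is out of reach with that gate.

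**Where the power goes.** At a true ORR of 21%, exactly 1 response in 12 has probability 0.1885. A cohort allowed to continue from there reaches 5 of 41 with probability 0.8861. The product, 0.167, is the whole loss of 16.7 percentage points.

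**The case against.** The best reply is that the documents largely settle the matter. The rule of 1 appears in the design section, in all three statistical sections that set a gate, and in SAP Section 4. Section 9.1.6, which is devoted to the interim analysis, closes the TNBC cohort only at zero responses, and the printed 0.54 equals 0.95^12. Against these stands one sentence at the end of a text on infusion reactions. Nothing suggests that 2 was ever applied, so the 74% power is hypothetical. The final test, the ORR estimate and its confidence interval do not change, and a protocol edit cannot alter a decision already made. A response count is a result and could go in the study report.

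Much of this stands. The note is very probably a drafting error, no calculation in the plan is wrong, and the documents do not show that the conflict arose in practice. But they give no order of precedence between sections, and the outlying sentence sits in operational text and presents the count as a condition for Stage 2. SAP Section 4 states the planned rule, not the rule applied. SAP Section 5.1 calls the completed analysis informal and says only that response rate was considered. The question of which threshold was used is therefore fair. Reporting the count with it would show at once whether the two rules could have led to different decisions.

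**Conclusion.** The inconsistency is real, and the note in Section 5.2.1.2.1 is the text to correct, because the stated 90% power and 0.54 early-termination probability can be obtained only with a gate of 1. If a gate of 2 was used, TNBC power falls from 0.906 to 0.739, early termination under the null rises from 0.540 to 0.882, and the chance of stopping a regimen with a true ORR of 21% at Stage 1 rises from 5.9% to 24.8%. Type I error is within 0.05 under both rules.

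These figures assume exact binomial sampling, 12 and 29 evaluable subjects, and a futility rule that is followed as written. The Section 2.2 diagram was not legible in the text available, so its threshold is unchecked. Which gate governed the actual Stage 1 decision cannot be confirmed from the documents.

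**What to change.** 1. In Protocol Section 5.2.1.2.1, change the note to require at least 1 objective response in each tumor type, in line with Sections 2.1, 9.1.1, 9.1.3 and 9.1.6 and SAP Section 4.
2. Check that the Trial Diagram in Section 2.2 shows the same threshold.
3. In SAP Section 5.1, state which TNBC response threshold was applied at the completed Stage 1 analysis, and the number of TNBC responses among the 12.
4. Only if a gate of 2 was applied, restate TNBC power as about 74% and early termination under the null as 0.88.

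The cost is one line of protocol text (with whatever amendment step that requires), one figure check, and one or two sentences in the SAP. No patients or analyses are added.
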